10.2 Unanticipated Adverse Device Effect (Event)

An Unanticipated Adverse Device Effect (UADE) will be defined as per FDA Regulation 21 CFR 812.3(s) as "any serious adverse effect on health or safety or any life-threatening problem or death caused by, or associated with, a device, if that effect, problem, or death was not previously identified in nature, severity, or degree of incidence in the investigational plan or application (including a supplementary plan or application), or any other unanticipated serious problem associated with a device that relates to the rights, safety, or welfare of subjects".

As per FDA regulations 21 CFR §812.150(a)(1), §812.46(b), and §812.150(b)(1), all UADEs must be reported by the clinical investigator to the sponsor and the reviewing IRB, as described below:

- An investigator is required to submit a report of a UADE to the sponsor and the reviewing IRB as soon as possible, but in no event later than 10 working days after the investigator first learns of the event (§ 812.150(a)(1)).
- The sponsors must immediately conduct an evaluation of a UADE and must report the results of the evaluation to FDA, all reviewing IRBs, and participating investigators within 10 working days after the sponsor first receives notice of the effect (§§ 812.46(b), 812.150(b)(1)).

10.3 Actions in Response to Adverse Events

During training, the study team member will learn the appropriate actions to take in response to an adverse event. These actions may include, but are not limited to:

- **Suspending COOLSTAT Cooling:** COOLSTAT cooling may need to be removed from the subject at the discretion of the investigator or their designee. This would involve stopping the air flow and removing the nasal mask, but otherwise keeping the device on and continuing to collect temperature data for the study period.
- **Switching to Alternative Cooling Method:** The investigator or their designee may switch the subject onto an alternative cooling method if it is deemed necessary for the subject's safety; the subject will be completely removed from the COOLSTAT device. Manual data will continue to be collected for the following 22 hours.
- **Removing the Device Without Alternate Cooling:** The COOLSTAT can be completely removed from the subject without starting alternate cooling if, at the discretion of the investigator or their designee, the safety of the subject is at risk and/or cooling is no longer needed.

10.4 Anticipated Adverse Events

- Nose bleeds (epistaxis)
- Shivering
- Pressure or skin breakdown because of mask
- Aspiration
- Nasal congestion
- Over-cooling
- Insufficient cooling
- Increase in insensible losses (subject dehydration)
- Induced brain hypothermia
- Adverse effects on systemic blood pressure

10.5 Serious Adverse Events

- Severe nasal mucosal ulceration
- Severe oral mucosal ulceration
- Uncontrolled epistaxis requiring stopping of therapy or intervention
- CSF rhinorrhea
- Any other potentially life threatening event requiring immediate intervention
- Any other unanticipated device related adverse event.

10.6 Technical Device Failures

Technical device failures will be recorded on a device performance CRF, and evaluated for possible adverse effects for the patient. For the purposes of this study, a technical device failure is defined as a failure of the COOLSTAT system to perform its intended function when used in accordance with the Instructions for Use, or to perform any aspect of the study protocol.

If a device failure results in an adverse experience for the patient, this adverse experience should be recorded on the Adverse Event Form. Device failures that do not result in an adverse effect for the patient will be noted on the device performance report form, but will not be considered an adverse event in and of themselves.

10.7 Warnings

Note: These warnings are specific for the investigational device.

- Use of the COOLSTAT device should only be undertaken by a study team member who is thoroughly familiar with the proper use of the device as provided in all provided instructional and guidance documents, and only under the supervision of the clinical investigator.
- Do not attempt to service the COOLSTAT device. COOLSTAT includes potentially hazardous moving parts and the risk of electrical shock if the device cover is removed. Contact CoolTech for all servicing needs.
- The COOLSTAT device should only be used with appropriately grounded electrical outlets.
- When setting a target temperature, the user should exercise care and proper device procedures to avoid incorrect therapy – the COOLSTAT device may have the ability to overcool the patient below normothermia temperatures.

10.8 Precautions

Note: These precautions are specific for the investigational device.

- Proper placement of the core temperature sensor is important for COOLSTAT to appropriately cool subjects – clinicians are responsible for properly placing the

sensor in accordance with standard practice. Esophageal, SpotOn, and bladder temperature probes are acceptable core temperature sensors for use with COOLSTAT.

- COOLSTAT disposables are for single subject use only. Do not reuse and do not use with multiple subjects.

10.9 Follow-up of Unresolved Events

Any unresolved adverse events, adverse device effects and/or unexpected adverse device effects still unresolved when the subject ends the study will be followed until they are resolved but no longer than 24 hours.

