Statistical Methodology	
The primary efficacy analysis for temperature maintenance will be based on the evaluable population of subjects who achieve normothermia by 4 hours and continue cooling treatment with the COOLSTAT System.
 
The proportion of subjects fulfilling success criteria and 90% confidence intervals will be reported and compared to the a priori minimum acceptable criteria:
 
 • at least 75% of the subjects will reach normothermia (core temperature $\leq 37.5^{\circ}\text{C}$) within 4 hours of starting COOLSTAT cooling, and • at least 75% of the subjects' core temperatures remain between 36°C and 37.5°C for 80% of the steady state time following the initial achievement of 37.5°C. 
All adverse events (AEs) reported during the study will be presented in tabular format to include: time of onset, whether or not the patient continued in the study, the nature of intervention and resolution. The potential contribution to the AE by the device will be assessed by the attending physician who reports the AE and the investigator.

Data Safety Monitoring Board	
A DSMB will be formed to monitor this study. The DSMB will meet: 1) before any subjects are enrolled (to review the study), 2) after the first 5 subjects (all with ICP monitoring), 3) after the first 10 subjects (before proceeding to 24-hour

upon being reconnected to the CoolStat is $\leq 37.5^{\circ}\text{C}$. If the subject's temperature is $> 37.5^{\circ}\text{C}$ upon being reconnected to the device, the device will be given up to an additional 4 hour-period to bring the patient to normothermia ($\leq 37.5^{\circ}\text{C}$). Once the subject's core temperature is $\leq 37.5^{\circ}\text{C}$, the device will be considered in steady state.

cooling treatment), 4) after each 6-month period of study, 5) at the end of the study, and 6) after any serious adverse event.

A clinical monitor will also be used to periodically visit the study sites and monitor the activities of the study to ensure that the study protocol, consent activities and data collection are being completed in accordance with specified procedures.

The Clinical Monitor and DSMB will be comprised of:

- [name] - Clinical Monitor
- [name] (Johns Hopkins) - Chair of DSMB - Voting Member
- [name] (Johns Hopkins) - DSMB Voting Member
- [name] (UMMC) - DSMB Voting Member
- [name] (UMMC) - DSMB Voting Member
- [name] (UMMC) - PI (Non-Voting Member)

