6.4 Safety Outcomes

An important outcome of this study is to assess the safety of high flow rate transnasal air delivery by the COOLSTAT device. The device safety will be addressed by the following:

³ This recognizes that some subjects will have short periods of break-through fever over the course of the study.

- The incidence and severity of all adverse events (including non-device-related adverse events) and the potential contribution to the adverse event that may be device related.
- Assessment by the investigator or their designee and attending physician(s) as to any adverse event that may be related directly to transnasal cooling.
- Confirmation based on a visual exam of the turbinates and upper airway that no clinically significant abnormal findings were attributable to transnasal air flow or the COOLSTAT device.

This study should also demonstrate that the COOLSTAT system can perform in the clinical setting.

The study may provide insight into the incidence of shivering, although the study design is not sufficiently powered to expect definitive conclusions.

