9.4 Phase 2 – Post-Therapy Monitoring Phase

After Phase 1, the COOLSTAT will be stopped by pressing the 'Start/Stop' button on the control panel of the device. Once the device is in the pause mode, the nasal mask will be removed from the subject and the temperature probe disconnected from the COOLSTAT, however, the hospital core temperature sensor will remain connected to the subject, or it can be replaced with the esophageal, SpotOn, or bladder sensor at the discretion of the PI. This will conclude any cooling with the COOLSTAT. Manual data collection will continue for two hours after COOLSTAT cooling has concluded to capture the subject's response post-cooling.

Any new cooling therapies can be applied to the subject as directed by clinicians, but will need to be noted in the case report forms. Phase 2 ends at the conclusion of this two-hour observational period. The COOLSTAT must be prepared for the next subject according to the procedures in Section 9.8.

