9.5 Phase 3 - Post-Cooling Follow-up

For the next 22 hours, the subject's vital data will continue to be manually collected every 4 hours, and a qualified board-certified otolaryngologist or otolaryngology resident (under the supervision of a board-certified otolaryngologist) will perform a follow-up examination of the upper airways within 24 hours of the end of Phase 1 COOLSTAT Therapy. The intensivist will perform the post-therapy nasal exam if an otolaryngologist is not available.

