9.9 Subject Study Completion

The study Subject Completion Form section of the therapy case form is to be completed after 22 hours of additional follow-up (end of Phase 3).

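### Section 10.9 stops outcome follow-up of open adverse events after at most 24 hours, even serious or device-related ones, so those still open can be tabulated only as unresolved

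*Combined protocol and SAP*

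**What the plan says.** Section 10.9 covers "Any unresolved adverse events, adverse device effects and/or unexpected adverse device effects still unresolved when the subject ends the study". These "will be followed until they are resolved but no longer than 24 hours". The rule is the same for a mild unrelated event, a serious event and a device effect, and no other section sets longer outcome follow-up for any of them.

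The Statistical Methodology row of the Summary (1.0) describes the output: a table of all adverse events giving "time of onset, whether or not the patient continued in the study, the nature of intervention and resolution".

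The timing comes from Section 9. In Phase 2, "Manual data collection will continue for two hours after COOLSTAT cooling has concluded" (9.4). Phase 3 adds 22 hours, and the subject completion form is filled in at its end (9.9). During Phase 3 the subject has an "examination of the upper airways within 24 hours of the end of Phase 1 COOLSTAT Therapy" (9.5; Section 13.3.1 gives the same limit).

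**The concern.** The table is meant to show how each event resolved, but the follow-up rule stops collecting that information on a fixed clock, whatever the nature of the event. The post-therapy examination looks for mucosal ulceration, bleeding and septal perforation (13.3.1), and severe nasal or oral ulceration is a listed serious event (10.5). The protocol gives no reason why one further day should be enough to learn the outcome of such findings.

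What is at stake is how the safety results can be read. The objective is safety and performance (6.2). Only 30 subjects are treated, and the 20 double nostril and 10 single nostril subjects are to be analysed separately (13.0). With groups of this size, one local injury of unknown outcome is a visible part of the safety record.

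**Working it through.** No sample size, power or error rate enters this point, and the plan states no figure to reproduce. The check is a sum of stated durations and a comparison of the follow-up rule with the planned output.

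**Inputs**

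| Item | Value | Source |
|---|---|---|
| Phase 2 | 2 h | 9.4 |
| Phase 3 | 22 h | 9.5, 9.9 |
| Latest nasal examination | 24 h after cooling | 9.5, 13.3.1 |
| Cap on open events | 24 h | 10.9 |
| Cooling time | 8 h (subjects 1 to 10) or up to 24 h (the rest) | 6.10, 13.0 |

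**Step 1: study end.** 2 + 22 = 24 h after cooling stops.

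**Step 2: latest outcome follow-up.** Section 10.9 does not say outright when its 24 h begins. The natural reading is the subject's study end, which gives 24 + 24 = 48 h after cooling stops. An earlier starting point would shorten this.

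**Step 3: measured from the start of cooling**, without transport interruptions: 8 + 48 = 56 h for 8-hour subjects and at most 24 + 48 = 72 h for 24-hour subjects.

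**Step 4: follow-up left after the nasal examination.** For an examination *t* hours after cooling, at most 48 − *t* hours remain:
- *t* = 2: 48 − 2 = 46 h
- *t* = 24: 48 − 24 = 24 h

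So 24 h is the limit at the latest permitted examination time, and earlier examinations leave more.

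**Step 5: what the table can show.** An event that resolves before the cap can be reported in full. For an event still open at the cap, no later information is collected, so the only possible entry is unresolved. A lesion that heals the following week and one that never heals receive the same entry.

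**Step 6: whether another provision fills the gap.**
- Medical records are reviewed when an adverse event occurs (1.0, Data Collection). No review at a later date is required.
- The sponsor must evaluate an unanticipated adverse device effect and report within 10 working days (10.0, 10.2). This is a reporting duty. It can run well past the 48 h point, but no outcome data are required for that time.
- The DSMB meets after any serious adverse event (1.0, 14.5). Nothing requires that the event's outcome be obtained for it.

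**Step 7: weight of one event.** One event with unknown outcome is 1/30 = 3.3% of treated subjects and 1/10 = 10% of the single nostril group. This is an illustration only; the documents give no expected number of events open at the cap.

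**The case against.** The strongest case on the other side is that little is lost. Section 6.4 defines safety by incidence, severity, device contribution and examination findings, and Section 13.3.2 plans an assessment of cause. Resolution is one descriptive column, not an endpoint, and unresolved is a legitimate entry in it. The mask is also removed every 4 hours during cooling for inspection, so some visible nasal injury would be found earlier and observed for longer. All of this stands, and it limits the size of the point.

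A reader might infer more than the documents support:
- *That events disappear from the record.* Only outcome follow-up stops. Reporting, sponsor evaluation and DSMB review continue.
- *That the table as a whole cannot report resolution.* Only events still open at the cap are affected.
- *That every subject has only about 24 h of observation after the examination.* Step 4 shows that this holds only for the latest permitted examination.
- *That the DSMB would decide on continuation without information it needs.* The criteria for moving to 24-hour cooling (6.10) and for raising the flow rate (13.0) turn on whether events or findings occurred, not on whether they healed.
- *That the post-therapy examination is how CSF rhinorrhea would be found.* It is a listed serious event (10.5) but is not on that examination's checklist (13.3.1).

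It can also be said that chart review shows healing only if someone looked again and recorded it, and no later nasal examination is planned. That is fair. It does not defeat the remedy, because a dated entry of unresolved or unknown at discharge still tells the reader more than a follow-up that stopped at a fixed hour.

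**Conclusion.** The concern holds in a limited form. Section 10.9 is a stated rule, not a missing detail. For serious and device-related events still open at the cap, it discards outcome information that the planned table is meant to carry. Outcome follow-up ends at most 48 h after cooling, and a lesion first found at the latest permitted examination has at most 24 h. The consequence is that a transient local injury cannot be told from a lasting one.

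This rests on two assumptions: that the cap runs from the end of Phase 3, and that the Adverse Event Form, other case report form templates and DSMB appendices, which are not in the documents available here, set no longer outcome collection. The number of events affected is not given and may be small. No stated safety endpoint, continuation rule or escalation rule is invalidated.

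**What to change.** Keep the 24-hour limit for events that are neither serious nor device-related. For serious or device-related events still open at the cap, record the outcome and its date from the hospital record at resolution or discharge, whichever comes first. Where the chart does not show resolution, enter unresolved or unknown at discharge, with the date. Show outcome and date in the adverse event table.

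The cost is a short chart review and later closure of the case report forms for the few affected subjects, with no added visit or procedure. Collection may run past the 7 to 10 days stated as each subject's study duration (1.0), so that statement needs a matching change. The sponsor should also check that consent covers the later chart review, since the consent pages were not available here. The change is a protocol amendment and needs FDA approval before use (14.15). It is a cheap improvement.

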11.0 Investigational Medical Devices

11.1 Description of Investigational Medical Devices

The investigational medical device will be labeled “CAUTION - Investigational Device. Limited by Federal (or United States) Law to Investigational Use”. This will help to ensure that the investigational products are not accidentally used for other non-trial related procedures. (Any original equipment manufacturers labeling will not be removed but shall be over-labelled for the purpose of the IDE labeling.)

11.2 Product Packaging and Labelling

The device (hardware/software) will not have a separate package. Labelling will be directly on its enclosure.

The disposables are split into two different packages – each set of tubing manifold and nasal mask is sealed in a plastic bag, and each desiccant cartridge is sealed in a heat seal foil pouch to protect from moisture. A photograph of disposable labels is included in the Operator’s Manual.

11.2.1 Device Operating Instructions

All safety and operational information are included in the Operator’s Manual.

11.2.2 Device Package Labels

The device labels will include the following information:

- “CAUTION – Investigational Device. *Limited by Federal (or United States) Law to Investigational Use.*”
- “COOLTECH LLC
[name]
[name]”

- Study name
- Device name
- Device serial number
- “Be familiar with device operation before use”

11.2.3 Disposable Package Labels

The disposable labels will include the following information:

- “CAUTION – Investigational Device. *Limited by Federal (or United States) Law to Investigational Use.*”
- “COOLTECH LLC
[name]
[name]”
- Lot number
- Expiration date (Use by date)
- “NON-STERILE”

11.3 Required Experience and Training

The investigators and any site personnel directly involved in the study or protocol execution must be trained in accordance with their responsibilities about the COOLSTAT device and protocol requirements at the study initiation visit; and whenever new investigator or study personnel are added. The training will be documented in the training case form. Only qualified personnel may handle the device.

11.4 Storage and Handling

The COOLSTAT device, the desiccant cartridges, and the mask disposable sets will be stored at room temperature and maintained by designated study personnel in a locked room. The equipment may only be handled by designated study personnel.

11.5 Accountability of Investigational Medical Devices

Receipt, use and return of the medical devices will be documented on a device transport log. Additionally, each subject’s therapy record case form must identify devices (hardware and disposables) specifying the device by serial number, and all reference numbers for disposables used. All “service” conducted per unit will also be maintained in a service record log maintained for each unit, including records of removal of any unit from the study premises for any reason. Each used disposable set must be accounted for on the transport log and by patient ID. Use and disposal of disposables will be recorded on CRFs (e.g. number of desiccant cartridges used). In the event of a desiccant cartridge or nasal mask malfunction or failure, the faulty item will be bagged and retained until communication with Sponsor to determine follow up procedures to failure mode analysis.

12.0 Data Collection and Management

12.1 Case Report Forms

The data for this study will be collected using Case Report Forms (CRFs), not including the data collected by the COOLSTAT device. Blank template forms are provided.

Prior to the start of the clinical trial, the study center will be provided with a sufficient number of Case Report Forms and these may be replenished as needed. All entries are to be made in blue or black ink and are to be legible. All information in the CRFs should be in English. All corrections made on paper based forms are to be completed by placing a single line through the incorrect data, leaving the incorrect data clearly visible (e.g. 352 325), and the individual making the correction must initial and date the correction. Erasure by any method is not allowed. The personal data recorded on all documents will be regarded as confidential.

The investigator will be responsible for the timely and accurate completion of specific CRFs (or certain areas on the CRF) for an individual subject for whom he/she may be responsible, wherein an investigator's signature is required. Where so designated trained study personnel may record information on case report forms.

Except for adverse event forms which have a limited time to be completed and forwarded, each set of CRFs for a specific subject must be completed as soon as practical as each subject completes (or is withdrawn from the study).

Completed CRFs shall be transmitted to the Sponsor in a timely manner. Original case forms shall be stored in a designated area convenient for the Monitor and Principal Investigator. The Principal Investigator shall review data from the study at any time throughout the course of the study. The monitor and PI may request data queries in the event of incomplete records or recording discrepancies.

12.2 Review and Query of Completed CRFs

Any corrections of data (by PI or Sponsor) after CRF pages have been collected will be done by way of a written query. The query should state the question or data to be clarified. The query and correction will be included with the Sponsor's copy of the CRF and retained together with the original CRF in the Principal Investigator's files.

The receipt of the scanned form must be verified by an alternative method, such as an email to indicate forms have been sent to the Sponsor. The exact method for transmission will be detailed in the Investigator's Manual and may change from time to time based

upon Sponsor and Investigator's needs. Any such changes shall be documented and approved by the Sponsor and PI in advance. In any case, the Principal Investigator shall retain the original and make the original Case Report Forms (with any associated data queries) available to the Sponsor's designated Monitor at each monitoring visit.

